13.4.6 Immunogenicity Assessment

Immunogenicity assessment to monitor the potential development of an anti-drug antibody (ADA) response will be performed before the lilotomab administration and at subsequent timepoints (see [Section 13.4.6.2](#)).

13.4.6.1 Part A, Phase I and IIa

In Part A, patients will be monitored locally for the development of ADA after treatment up to 12 months. The sampling for these patients will be at the following time points at screening

visit, and after Betalutin administration: 1, 3, 6, and 12 months (see [Table 6-5](#) and [Table 6-7](#)). The exact date point when the sample is taken needs to be recorded in the eCRF.

A volume of approximately 9 mL of peripheral blood will be collected in a serum tube at patient screening. The serum will be collected at each study centre and used to assess the presence of pre-existing ADA (HAMA) locally using the Milenia® QuickLine HAMA test (Milenia Biotec), except for patients screened at the Radium Hospital (Oslo, Norway). In this specific case, the IFMA test will be used. When a positive result is obtained with the Milenia QuickLine HAMA test, a serum sample could be sent to the Radium Hospital for confirmation of the positive result with the IFMA test. Centres in Norway and Sweden may also ship serum samples to the Radium Hospital for further ADA testing, when feasible.

13.4.6.2 Part B FL Phase IIb and Part C Pharmacokinetic Cohort phase IIa

All patients included in Part B and Part C of the LYMRIT 37-01 study will be monitored for the development of ADA after treatment up to 12 months.

The blood sampling for these patients will be at the following time points:

- before lilotomab dose (Day-1/0, baseline), and
- after Betalutin administration: 7 days, and 1, 3, 6, and 12 months (see [Table 6-8](#)).
- Additional sampling will be required if a test is found ADA positive at 12 months. Persistence of the ADA response will then be assessed every 6 months until the ADA test is negative [46].

The exact time point when the sample is taken need to be recorded in the eCRF.

A volume of approximately 6 mL of peripheral blood will be collected by venipuncture in a dedicated serum tube at each time point (see above) to monitor the development of an ADA response post lilotomab/Betalutin treatment. Serum samples will be isolated, aliquoted and frozen in cryovials at -20⁰C at each study centre until shipment on dry ice the day after collection to the central biobanking laboratory at Covance Central Laboratories (Indianapolis, Indiana for US patients and Geneva, Switzerland for non-US patients), where they will be biobanked for future use.

Instructions for handling procedures, preparation, storage and shipping of the serum samples will be provided in the study Covance laboratory manual.

13.4.7 Volume of Blood to be Drawn from each Patient

The total volume of blood that will be drawn from each patient in this study will vary depending on how long the patient stays on study. [Table 13-3](#) and [Table 13-4](#) indicates the range for patients during the treatment period (16 weeks).

Table 13-3 Volume of Blood to be drawn from Each Patient in the Treatment Period – Part A (phase I and phase IIa)

Assessment	Sample Volume (mL)	No. of Samples	Total Volume (mL)
Serum biochemistry/haematology/lymphocytes subset	7 mL	Max 14	98 mL
Pharmacokinetic – Total radioactivity (phase I; optional for phase IIa)	1 mL	Max 17	17 mL
Immunogenicity assessments	9 mL	4	36 mL
Immunoglobulin levels/	5 mL	1	5 mL
Total (maximum volume to be drawn)			156 mL

Max = maximum number of samples to be taken

Table 13-4 Volume of Blood to be drawn from Each Patient in the Treatment Period – Part B and Part C

Assessment	Sample Volume (mL)	No. of Samples	Total Volume (mL)
Serum biochemistry/haematology/ lymphocytes subset	7 mL	Max 14	98 mL
Coagulation parameters	6 mL	2	12 mL
β-HCG pregnancy test	6 mL	1	6 mL
HAMA test	4 mL	1	4 mL
Pharmacokinetic – Total radioactivity in blood	2 mL (1 mL exactly in assay)	Max 11	22 mL
Pharmacokinetics – Total lilotomab antibodies in serum	4 mL	Max 15	60 mL
Immunogenicity	6 mL	4*	24 mL
HLA haplotyping	2 mL	Max 1	2 mL
Immunoglobulin levels/	5 mL	2	10 mL
Total (approximate maximum volume to be drawn for patient not participating in the PK portion of Part B)			158mL
Total (approximate maximum volume for the patients participating in the pharmacokinetic portion of Part B and all patients in Part C)			240mL

Max = maximum number of samples to be taken; *immunogenicity samples continue at months 6 and 12 – and if ADA positive at month 12, further samples will be required.

13.4.8 Potential Long-term Toxicity

At the follow-up visits the investigator will observe for indications of potential late-toxicity, such as secondary cancers, acute myelogenous leukaemia, myelodysplastic syndrome, and aplastic anaemia. In addition, physical examination will be performed and blood samples for biochemistry and haematology taken. Potential long-term toxicity (new onset AESIs, and study treatment-related AEs and SAEs only with onset >12 weeks after the last administration of study treatment) must be reported according to Section 13.2.

13.4.9 Quality of Life (Part A and Part B)

QoL will be assessed using FACT-Lym (Version 4), which will be completed by the patient. The form will only be used in the countries where they are translated and validated. It is essential to explain to the patient that all parts of the questionnaire should be completed as fully as possible. In order to administer these consistently, the questionnaire will be completed by the patient at the hospital visit.

QoL is not collected from patients entered to Part C.

14 STATISTICAL METHODS AND PLANNED ANALYSES

14.1 Statistical Hypotheses and Tests

14.1.1 Sample Size Calculation – Part A (phase I and phase IIa)

The phase I design is a “3+3” design, where MTD is defined as highest dose where ≤ 1 of 6 patients experience DLT. The number of patients will depend on the number of dose levels explored and are expected to be up to approximately 40 patients, depending on occurrence of DLTs. The patient will be substituted if the data are insufficient.

For Arm 1: Due to the limited number of patients treated in phase I (six), an interim analysis of the safety and efficacy of lilotomab 40 mg/ Betalutin 15 MBq/kg was performed after 9 additional patients had been treated in phase IIa (total: 15 patients).

The following guide was used for the Arm 1 interim analysis, and the final decision was taken by the SRC:

- If ≥ 4 DLT in 15 patients -> lower the dose
- If ≤ 3 DLT in 15 patients -> continue on same dose (or see below)

In addition, response rate will be evaluated for futility:

- If ≥ 4 responses in 15 patients -> continue on same dose
- If ≤ 3 responses in 15 patients -> stop for futility (or see below)

It will be opened up for a combined evaluation:

- If ≥ 4 DLT and ≥ 7 responses -> lower the dose
- If ≤ 3 DLT and ≤ 10 responses -> increase the dose to 20 MBq/kg Betalutin based on the recommendation of the SRC analysis of the observed toxicities.

The decision to continue the dose was made by the SRC. Thirty more patients were planned in Part A, phase IIa for a total of 36 patients at that dose level.

Following a review of the Arm 4 phase I patient safety data by the SRC, approximately 10 to 15 additional patients will be enrolled into a Part A, phase IIa expansion arm and be treated with 20 MBq/kg Betalutin and 100 mg/m² lilotomab.

14.1.2 Sample Size and Statistical Hypotheses – Part B (phase IIb) Follicular Lymphoma

14.1.2.1 Randomised Part B - Choice of RP2D

Note - Part B of the study was initiated as a randomised, 2-arm, open-label study to further differentiate the risk/benefit of 2 promising dose regimens of lilotomab and Betalutin. (Protocol Version 11)

In total, up to 130 patients (65 patients per candidate regimen) with FL will be enrolled.

Based on data available at time of Protocol Version 11, a difference of 27% in ORR is expected to emerge between the dose regimens with similar low toxicity profiles. The ORR's assumed

for each group are: 69% for the 40 mg lilotomab+15 MBq/kg Betalutin arm, and 42% for the 100 mg/m² lilotomab+20 MBq/kg Betalutin arm.

A sample size of 65 patients per arm should be sufficient to detect this difference, using a two-sided significance level 0.05 with at least 80% statistical power. Sample size estimation was performed using nQuery Advisor V7 (Statsol.com). The method was a 2 group continuity corrected chi-square test for equal proportions (55).

14.1.2.2 Interim Analysis – Part B Randomised

Note - The interim analysis was introduced in Protocol Version 11 and amended in protocol Version 13.

Once approximately 50 patients have been treated (approximately 25 per dose regimen), an interim analysis will be performed on the ORR based on IRC assessment for the study. There is no statistical test of hypothesis in the interim analysis.

In line with its charter, the SRC will review the results of the interim analysis and provide a recommendation to the Sponsor to continue or terminate treatment arms or to perform other modifications based on the totality of safety, efficacy, and other available data (e.g. immunogenicity data). The final decision lies with the sponsor.

The SRC will take into account the following guidelines: if ORR \geq 40% in each treatment regimen, the study may complete its targeted enrolment of up to 130 patients, around 65 per arm. If ORR < 40% in either regimen then the regimen with ORR <40% may be terminated. If both regimens have ORR <40%, the study may be terminated for futility or modified. There regimen(s) with ORR \geq 40% will proceed to enrol the remaining patients, up to 130 total.

To facilitate decision to keep or drop treatment arms based on ORR rates, the boundary of 40% ORR is non-binding and for guidance only.

The primary efficacy endpoint is overall tumour response rate according to the IRC. Scans will be performed at baseline, 3, 6, 9, 12, 18, 24, 36, 48 and 60 months after Betalutin injection for all patients to assess tumour response (see [Section 14.1.7](#)).

Response rates will be presented as a percentage of the Intent-to-Treat (ITT) population with the exact 95% confidence interval (Clopper-Pearson).

14.1.2.3 Part B – Population treated with “40/15” Regimen

Note - At the interim analysis, the SRC decided to discontinue the “100/20” treatment regimen, and continue with further recruitment in the “40/15” treatment regimen only.

A total of 87 patients, including the those from the interim analysis, will be recruited and treated with the “40/15” regimen.

With 87 patients, there will be more than 90% power to detect a difference of 18% in response rates using a two-sided exact test with a target significance level of 0.05, assuming the response rate under the null hypothesis is 30% and the response rate under the alternative hypothesis is 48%. If there are at least 36 responders in 87 patients, then there will be at least 97.5% chance that the true response rate will be at least 30%.

Moreover, with 87 patients, there will also be more than 90% power to detect a difference in complete response rate of 8% under the null hypothesis versus 20% under the alternative hypothesis.

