4.8.10 Outcome of the Interim Analysis on Patients Entered to Part B

The SRC reviewed efficacy and safety data for 47 patients who had been observed for a minimum of 3 months after Betalutin treatment. Based on the outcomes assessed and the totality of safety and efficacy, including the ORR and overall safety data including haematological adverse events, the SRC recommended that all future patients receive the regimen of lilotomab 40 mg and Betalutin 15 MBq/kg (“40/15”). There will be Betalutin dose adjustments for the first patients with a prior autologous-SCT and/or platelet count $\geq 100 \times 10^9/L$ but $< 150 \times 10^9/L$ as follows:

- Patients with a prior autologous SCT and platelet count $\geq 150 \times 10^9/L$ will receive Betalutin at the reduced dose of 12.5 MBq/kg.
- Patients with a prior autologous SCT and platelet count $\geq 100 \times 10^9/L$ but $< 150 \times 10^9/L$ will receive Betalutin at the reduced dose of 10 MBq/kg.
- Patients without a prior autologous SCT, and platelet count $\geq 100 \times 10^9/L$ but $< 150 \times 10^9/L$ will receive Betalutin at the reduced dose of 12.5 MBq/kg.

The SRC will review the safety data of the first 3 patients in each subpopulation and will further guide the determination of the recommended dose regimen for these subpopulations.

4.8.11 Rationale for Lower Betalutin Dose for Patients with Prior Autologous-SCT and/or Lower Platelet Level (Part B)

Discussion with the SRC, investigators and lymphoma experts (amendment implemented in protocol Version 14) lead to recommendation that:

- The revised inclusion criteria for platelets should not allow for the acceptable platelet threshold to be lowered too much on grounds that many of the DLTs in Part A were bleeding related.

Elderly patients who have cycled through previous therapies for FL and could potentially be treated on this protocol sometimes have platelets that are lower than would be considered ‘normal’ in younger, healthier reference populations. In order that this protocol includes a more representative population of FL patients there is a desire to include patients with platelets that are $\geq 100 \times 10^9/L$. This threshold represents a compromise between the desire to be more inclusive and the potential threat from radiation induced thrombocytopenia which is a recognised and reproducible AE with this therapy.

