14.1.7 Analysis of Efficacy Data

Tumour response will be reported as follows in individual patients:

- CR
- PR
- SD
- PD
- NE

In Part A and Part C: Response rate will be presented as a point estimate of the proportion of responders along with the 95 % exact confidence interval of response rate.

In Part B randomised period: The ORR will be compared between dosing regimens using the Fisher's Exact test, and the difference in response rates and the corresponding 95% exact CI will be presented. ORR estimates and 95% exact CI for each dosing regimen will also be presented.

In Part B Single-arm 40/15 part: – The primary efficacy analysis on ORR (based on independent assessment) will be performed by testing whether the ORR is less than or equal to 30% against the alternative hypothesis that ORR is greater than 20% at overall two-sided 5% level of significance, i.e.,

$H_0: p = 0.3$ vs. $H_a: p \neq 0.3$

In addition, the secondary efficacy analysis on CRR (based on independent assessment) will be performed by testing whether the CRR is less than or equal to 8% against the alternative hypothesis that ORR is greater than 8% at overall two-sided 5% level of significance, i.e.,

H0: $p = 0.08$ vs. Ha: $p \neq 0.08$

Responders are defined as having CR and PR according to definition in [Section 12.3](#).

Time to event endpoints will be analysed using standard Kaplan-Meier techniques. The estimate of the median survival curve will be calculated along with the associated 95% confidence intervals (when applicable). The efficacy endpoints are:

Overall Response Rate (ORR)

ORR, defined as the proportion of patients who achieve a CR or PR assessed with the use of standard criteria for lymphoma (1). The ORR will be assessed at 3 months image evaluation.

Best ORR will also be evaluated, taking the best response achieved independent of time point for image evaluation.

Complete Response Rate (CRR)

CRR, defined as the proportion of patients who achieve a CR assessed with the use of standard criteria for lymphoma (1). The CRR will be calculated based on complete responses achieved at any timepoint.

Progression-free survival (PFS)

PFS is defined as the interval from Betalutin administration and date of:

- Relapse (new or enlarged lesions after CR).
- Progression (new or enlarged lesions after PR or SD).
- Death from any cause.

If none of the above events are observed, PFS will be censored at the date of the last adequate tumour assessment

Duration of response (DoR)

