3.2.2 Efficacy Analysis set

Efficacy Analysis set will be a subset of the Part B participants who received Betalutin and were assigned either “40/15” or “100/20” dose levels.

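### The pooled 40/15 ORR and CRR include interim patients whose responses helped select 40/15, so the estimate leans upward (about 1 to 2 points if the higher ORR decided the choice), and the SAP neither separates these patients nor says so

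*Protocol*

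**What the plan says.** **Selection.** Part B randomised patients 1:1 between 40/15 and 100/20. Protocol 14.1.2.2 planned an interim look at IRC-assessed ORR after about 50 patients. It had no hypothesis test and a non-binding 40% guide for keeping or dropping a regimen. The look took place at 47 patients. Protocol 4.8.10 gives the basis for choosing 40/15: "Based on the outcomes assessed and the totality of safety and efficacy, including the ORR and overall safety data including haematological adverse events". Protocol 4.8.11 reads the interim result as favouring 40/15 on efficacy, with adherence and safety also cited.

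**Reuse in the protocol.** The Version 15 summary of changes shows that the single-arm hypothesis and sample size were set after that choice. Protocol 14.1.2.3 then states: "A total of 87 patients, including the those from the interim analysis, will be recruited and treated" with 40/15. It plans a "two-sided exact test with a target significance level of 0.05", with a null ORR of 30% and an alternative of 48%. Protocol 14.1.7 places the test "at overall two-sided 5% level of significance".

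**Reuse in the SAP.** Section 3.2.2 says: "Efficacy Analysis set will be a subset of the Part B participants who received Betalutin" and were assigned 40/15 or 100/20. Interim patients are not set apart. Section 3.7.1.2 reports ORR with a Clopper-Pearson 95% interval, and 3.7.2.2 treats CRR in the same way. Section 2.4 says the terminated study is not powered for its original objectives and will be summarised and listed. Neither document contains an adjustment for selection, a separate analysis of later patients or a caveat.

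**The concern.** When a regimen is kept partly because its early response rate looked good, those early responses are on average somewhat too favourable to it. Patients treated later do not carry that particular bias. Pooling the two groups dilutes the bias without removing it, and a Clopper-Pearson interval assumes that no selection took place. This concerns the 40/15 figure on its own and does not depend on any comparison with 100/20. Stopping short of 87 patients raises the share of the sample that was used for selection. The close-out report will present the pooled ORR as its primary result, and its reader will have no means of judging how far selection matters.

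**Working it through.** **1. The plan's own figures.** Exact binomial, 87 patients, null 30%, alternative 48%. Protocol 14.1.2.3 says "there will be more than 90% power to detect a difference of 18% in response rates" and gives its threshold in a clause beginning "If there are at least 36 responders in 87 patients".
- Pr(X ≥ 36 | 0.30) = 1.57%, and Pr(X ≥ 36 | 0.48) = 91.1%.
- The Clopper-Pearson lower limit is 30.9% for 36/87 and 29.9% for 35/87, so 36 is the correct threshold.
- The lower rejection region is 17 or fewer responders, with probability 1.91%. The unselected two-sided error is therefore about 3.5%.

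The stated power and threshold are reproduced.

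**2. Inputs for the selection check.**
- Interim size 47 (Protocol 4.2.3). The split is not given. I assume 24/23 and 23/24, with 25/25 as a check.
- Final size 87 (Protocol 14.1.2.3), or 61 as an illustration. The 61 is the number reviewed in July 2022 (SAP section 1), not a stated final sample size.
- Main scenario: true ORR 30% in both arms, the arm with the higher interim ORR kept, ties split evenly.

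**3. Formulae.** Let n₁ be the 40/15 patients at interim, X₁ their responders and N the final size.
- Bias of the pooled ORR = (n₁/N) × [E(X₁/n₁ | 40/15 selected) − p].
- Upper-tail error given selection = Σₓ Pr(X₁ = x | selected) × Pr(Bin(N − n₁, 0.30) ≥ c − x), with c = 36 for N = 87 and c = 26 for N = 61. The lower limit for 26/61 is 30.04%, the first to exceed 30%.

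**4. Higher ORR kept.** By exact enumeration, the bias in the interim 40/15 patients alone is 5.66 points (24/23) or 5.07 points (23/24). Pooled:
- N = 87: 24/87 × 5.66 = 1.6 points; 23/87 × 5.07 = 1.3 points.
- N = 61: 24/61 × 5.66 = 2.2 points; 23/61 × 5.07 = 1.9 points.

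| | Unselected upper tail | Upper tail given selection | Lower tail given selection | Two-sided total given selection |
|---|---|---|---|---|
| N = 87 | 1.6% | 2.5–2.7% | 0.6–0.7% | 3.2–3.3% |
| N = 61 | 2.5% | 4.1–4.5% | 0.5–0.7% | 4.8–5.0% |

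The 25/25 split falls inside these ranges. The interim share rises from 24/87 = 28% to 24/61 = 39%.

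**5. Other scenarios.**
- True ORRs of 69% and 42%, the planning values in Protocol 14.1.2.1: 40/15 is picked about 97% of the time, and the pooled bias is 0.1 point at N = 87 and 0.2 at N = 61.
- Choice made on grounds unrelated to ORR: bias 0.
- Higher ORR and also at least 40% at interim, true ORR 30%: bias given selection is +4.0 to +4.4 points (N = 87) or +5.7 to +6.3 (N = 61). At N = 87 the upper tail given selection is 6.1–7.4%. The overall chance that either regimen is selected and then wrongly declared above 30% is 1.8–2.1%, because both arms usually fail the hurdle.

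I did not put a figure on the CRR bias. Every complete response is also a response, so it runs in the same direction, but its size depends on how closely CR and ORR move together.

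**The case against.** The strongest reply is that this is a small effect in a descriptive close-out analysis. The 40% guide was non-binding, and 14.1.2.2 does not say that the higher ORR wins: if both arms reached 40%, both could continue. Safety weighed in the choice. Equal true ORRs are an unfavourable assumption and contradict the protocol's own planning values. The interim review required at least 3 months of observation, whereas SAP 3.7.1.1 counts best response at any time, so selection on an early ORR would carry over only in part. All of this stands, and it is why the size is given as a range that includes zero.

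A reader might infer that the stated 5% level is broken. The documents do not support that. Under pick-the-winner the two-sided total stays at or below 5.0%, because the exact test is conservative and selection shrinks the lower tail. Only the upper tail given selection rises. The level is clearly passed only given that a strict 40% hurdle was applied and cleared, and the protocol describes no binding hurdle. The SAP has also dropped the test.

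A reader might equally treat the later patients as a clean reference. They are free of the interim selection, but SAP section 1 says the decision to terminate followed an efficacy review of 61 patients on 40/15, as well as slow recruitment. That could move both figures, possibly downward.

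SAP 3.10 says the abbreviated report will also carry interim results from other sources. That is not a substitute for a split: it is unclear whether it means the 47-patient interim or the July 2022 review, and neither need use the SAP's best-response definition.

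**Conclusion.** The point holds as a matter of estimation and labelling. The 40/15 ORR and CRR include patients whose ORR helped select the regimen, the interval ignores this, and nothing tells the reader. The bias is about 1 to 2 points if the higher ORR decided between equally effective regimens, near zero if 40/15 was truly much better or safety decided, and about 4 to 6 points only if a strict 40% hurdle was applied and passed. These figures rest on an assumed split of about 24/23, a purely ORR-based rule and the same ORR definition at interim and final analysis. The error-rate aspect concerns the protocol's test only, and there it is a shift into the upper tail, not a breach of the two-sided 5%. Fixing the 30% null and the 87 after the interim is a further dependence on the data that cannot be quantified from the documents.

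**What to change.** In SAP 3.7.1.2 and 3.7.2.2, add a row beside the pooled result giving ORR and CRR with exact 95% intervals for 40/15 patients who were not among the 47 in the interim analysis. Label it supportive. Define the group by interim membership, not by enrolment date, so that a patient treated before the decision but not used in it is kept.

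Add a note that the pooled estimate and interval include patients used to select the regimen and are not adjusted for this, and that the July 2022 efficacy review before termination may affect both rows. Give the number of 40/15 patients at the interim, so that the share can be seen.

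The cost is one row per table and a wider interval. If 61 − 24 = 37 patients remain, 18/37 responders gives 31.9% to 65.6%, against 34.6% to 60.7% for 29/61 pooled.

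I would not make any statement about exceeding 30% depend on the new row. Power at 48% would fall from 91% to about 79–83% with 62 to 64 patients, or 53% with 37, which is too much to give up for a bias of this size.
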